11.3.4. Analysis Visit Windows

For vital sign assessments (except weight):

Scheduled Visit	Target Study Day of Visit	Slotting Intervals
Pre-therapy		
Screening (Week -2)	-14	Not applicable
Baseline (Week 0)	1	Not applicable
On-therapy		
Week 1	8	2 to 11 days
Week 2	15	12 to 18 days
Week 3	22	19 to 25 days
Week 4	29	26 to 32 days
Week 5	36	33 to 39 days
Week 6	43	40 to 46 days
Week 7	50	47 to 53 days
Week 8	57	54 to 60 days
Week 9	64	61 to 67 days
Week 10	71	68 to 74 days
Week 11	78	75 to 81 days
Week 12	85	82 to 92 days
Week 14	99	93 to 106 days
Week 16	113	107 to 120 days
Week 18	127	121 to 134 days

Scheduled Visit	Target Study Day of Visit	Slotting Intervals
Week 20	141	135 to 148 days
Week 22	155	149 to 165 days
Week 25	176	166 to 179 days
Week 26 (End of Treatment Visit)*	183	180 to (last dose date + 25 days)
Post-therapy		
Week 34**	239	>Last dose date + 25 days
8 Week Follow-up Visit**	Last dose date + 63 days***	>Last dose date + 25 days

* Week 26 is the end of treatment visit for those subjects completing the study per-protocol. For subjects who withdraw early from study treatment, the end of treatment visit will be assigned to an analysis visit based on the visit slotting algorithm using study day and therapy phase.
 
** Week 34 is the 8 week post-treatment follow-up visit for those subjects completing the study per-protocol. The 8 Week Follow-up Visit is the 8 week post-treatment follow-up visit for those subjects who withdraw early from study treatment. Both visits will be assigned based on the visit slotting algorithm using therapy phase.
 
*** The target study day for the 8 Week Follow-up Visit for subjects who withdraw early from study treatment is set to be 9 weeks (63 days) after last dose to correspond with the timing of the 8 week post-treatment follow-up for subjects completing the study per-protocol (where last dose is at Week 25 and the follow-up visit is at Week 34).
		

For ECG assessments:

Scheduled Visit	Target Study Day of Visit	Slotting Intervals
Pre-therapy		
Week -2	-14	Not applicable
Baseline (Week 0)	1	Not applicable
On-therapy		
Week 2	15	2 to 22 days
Week 4	29	23 to 43 days
Week 8	57	44 to 120 days
Week 26 (End of Treatment Visit)*	183	121 to (last dose date + 25 days)
Post-therapy		
Week 34**	239	>Last dose date + 25 days
8 Week Follow-up Visit**	Last dose date + 63 days***	>Last dose date + 25 days

* Week 26 is the end of treatment visit for those subjects completing the study per-protocol. For subjects who withdraw early from study treatment, the end of treatment visit will be assigned to an analysis visit based on the visit slotting algorithm using study day and therapy phase.
 
** Week 34 is the 8 week post-treatment follow-up visit for those subjects completing the study per-protocol. The 8 Week Follow-up Visit is the 8 week post-treatment follow-up visit for those subjects who withdraw early from study treatment. Both visits will be assigned based on the visit slotting algorithm using therapy phase.
 
*** The target study day for the 8 Week Follow-up Visit for subjects who withdraw early from study treatment is set to be 9 weeks (63 days) after last dose to correspond with the timing of the 8 week post-treatment follow-up for subjects completing the study per-protocol (where last dose is at Week 25 and the follow-up visit is at Week 34).
		

For lab assessments:

Scheduled Visit	Target Study Day of Visit	Slotting Intervals
Pre-therapy		
Week -2	-14	Not applicable
On-therapy		
Week 1	8	2 to 18 days
Week 4	29	19 to 43 days
Week 8	57	44 to 85 days
Week 16	113	86 to 148 days

Scheduled Visit	Target Study Day of Visit	Slotting Intervals
Week 26 (End of Treatment Visit)*	183	149 to (last dose date + 25 days)
Post-therapy		
Week 34**	239	>Last dose date + 25 days
8 Week Follow-up Visit**	Last dose date + 63 days***	>Last dose date + 25 days

* Week 26 is the end of treatment visit for those subjects completing the study per-protocol. For subjects who withdraw early from study treatment, the end of treatment visit will be assigned to an analysis visit based on the visit slotting algorithm using study day and therapy phase.
 
** Week 34 is the 8 week post-treatment follow-up visit for those subjects completing the study per-protocol. The 8 Week Follow-up Visit is the 8 week post-treatment follow-up visit for those subjects who withdraw early from study treatment. Both visits will be assigned based on the visit slotting algorithm using therapy phase.
 
*** The target study day for the 8 Week Follow-up Visit for subjects who withdraw early from study treatment is set to be 9 weeks (63 days) after last dose to correspond with the timing of the 8 week post-treatment follow-up for subjects completing the study per-protocol (where last dose is at Week 25 and the follow-up visit is at Week 34).
		

For immunogenicity assessments:

Scheduled Visit	Target Study Day of Visit	Slotting Intervals
Pre-therapy		
Baseline (Week 0)	1	Not applicable
On-therapy		
Week 2	15	2 to 22 days
Week 4	29	23 to 43 days
Week 8	57	44 to 71 days
Week 12	85	72 to 99 days
Week 16	113	100 to 127 days
Week 20	141	128 to 155 days
Week 24	169	156 to 176 days
Week 26 (End of Treatment Visit)*	183	177 to (last dose date + 25 days)
Post-therapy		
Week 34**	239	>Last dose date + 25 days
8 Week Follow-up Visit**	Last dose date + 63 days***	>Last dose date + 25 days

* Week 26 is the end of treatment visit for those subjects completing the study per-protocol. For subjects who withdraw early from study treatment, the end of treatment visit will be assigned to an analysis visit based on the visit slotting algorithm using study day and therapy phase.
 
** Week 34 is the 8 week post-treatment follow-up visit for those subjects completing the study per-protocol. The 8 Week Follow-up Visit is the 8 week post-treatment follow-up visit for those subjects who withdraw early from study treatment. Both visits will be assigned based on the visit slotting algorithm using therapy phase.
 
*** The target study day for the 8 Week Follow-up Visit for subjects who withdraw early from study treatment is set to be 9 weeks (63 days) after last dose to correspond with the timing of the 8 week post-treatment follow-up for subjects completing the study per-protocol (where last dose is at Week 25 and the follow-up visit is at Week 34).
		

For weight assessments:

Scheduled Visit	Target Study Day of Visit	Slotting Intervals
Pre-therapy		
Week -2	-14	Not applicable
On-therapy		

Scheduled Visit	Target Study Day of Visit	Slotting Intervals
Week 4	29	2 to 43 days
Week 8	57	44 to 74 days
Week 13	92	75 to 102 days
Week 16	113	103 to 127 days
Week 20	141	128 to 158 days
Week 25	176	159 to 179 days
Week 26 (End of Treatment Visit)*	183	180 to (last dose date + 25 days)
Post-therapy		
Week 34**	239	>Last dose date + 25 days
8 Week Follow-up Visit**	Last dose date + 63 days***	>Last dose date + 25 days

* Week 26 is the end of treatment visit for those subjects completing the study per-protocol. For subjects who withdraw early from study treatment, the end of treatment visit will be assigned to an analysis visit based on the visit slotting algorithm using study day and therapy phase.
 
** Week 34 is the 8 week post-treatment follow-up visit for those subjects completing the study per-protocol. The 8 Week Follow-up Visit is the 8 week post-treatment follow-up visit for those subjects who withdraw early from study treatment. Both visits will be assigned based on the visit slotting algorithm using therapy phase.
 
*** The target study day for the 8 Week Follow-up Visit for subjects who withdraw early from study treatment is set to be 9 weeks (63 days) after last dose to correspond with the timing of the 8 week post-treatment follow-up for subjects completing the study per-protocol (where last dose is at Week 25 and the follow-up visit is at Week 34).
		

For HbA1C assessments:

Scheduled Visit	Target Study Day of Visit	Slotting Intervals
Pre-therapy		
Week -2	-14	Not applicable
Baseline (Week 0)	1	Not applicable
On-therapy or post-therapy*		
Week 1	8	2 to 18 days
Week 4	29	19 to 43 days
Week 8	57	44 to 71 days
Week 12	85	72 to 99 days
Week 16	113	100 to 127 days
Week 20	141	128 to 162 days
Week 26 (End of Treatment Visit)	183	163 to 211 days
Week 34	239	>211 days

* For all subjects regardless their study drug discontinuation status, their on-therapy or post-therapy period assessments will be slotted in the same way to the appropriate analysis visits per the above defined slotting intervals.
		

For FPG assessments:

Scheduled Visit	Target Study Day of Visit	Slotting Intervals
Pre-therapy		
Baseline (Week 0)	1	Not applicable
On-therapy or post-therapy*		
Week 1	8	2 to 11 days
Week 2	15	12 to 18 days
Week 3	22	19 to 25 days
Week 4	29	26 to 32 days
Week 5	36	33 to 39 days

Scheduled Visit	Target Study Day of Visit	Slotting Intervals
Week 6	43	40 to 46 days
Week 7	50	47 to 53 days
Week 8	57	54 to 60 days
Week 9	64	61 to 67 days
Week 10	71	68 to 74 days
Week 11	78	75 to 81 days
Week 12	85	82 to 88 days
Week 13	92	89 to 102 days
Week 16	113	103 to 127 days
Week 20	141	128 to 162 days
Week 26 (End of Treatment Visit)	183	163 to 211 days
Week 34	239	>211 days
* For all subjects regardless their study drug discontinuation status, their on-therapy or post-therapy period assessments will be slotted in the same way to the appropriate analysis visits per the above defined slotting intervals.		

11.4. Appendix 4: Treatment Periods

For classifying AEs (including hypoglycemic events), the therapy periods will be defined as:

- **Pre-therapy:** The onset date of the AE is before the start date of randomized study medication. If the onset date of the AE is on the start date of randomized study medication, the AE will be considered as on-therapy.
- **On-therapy:** The onset date of the AE is on or after the start date of randomized study medication and within 25 days after the date of last dose.
- **Post-therapy:** The onset date of the AE is more than 25 days after the last date of randomized study medication.

For immunogenicity data and other safety parameters that are assessed prior to administration of randomized study medication on dosing days, the therapy periods will be defined as:

- **Pre-therapy:** The assessment date is on or before the start date of randomized study medication.
- **On-therapy:** The assessment date is after the start date of randomized study medication and within 25 days after the date of last dose.
- **Post-therapy:** The assessment date is more than 25 days after the last date of randomized study medication.

For an AE with an incomplete start date where the year and month are present while the day is missing, or where the year is present while both month and day are missing, the date is imputed in a dynamic way consistent with the partial date information so that the resulting AE therapy period assignment based on the imputed date is the most conservative possible, where the order from the most to the least conservative is: on-therapy phase > post-therapy phase > pre-therapy. Note that if the AE stop date is present, then the imputed start date will always be on or prior to the stop date.

11.5. Appendix 5: Derived and Transformed Data**11.5.1. Change from Baseline**

The baseline value for an assessment is defined as the last available nonmissing value prior to the first dose of the randomized treatment. Change from Baseline is defined as the postbaseline value minus the baseline value for the given assessment.

11.5.2. Body Mass Index Calculation

Body mass index (BMI) will be calculated as follows:

$$\text{BMI} = \frac{\text{weight (kg)}}{[\text{height (m)}]^2}$$

11.5.3. Total Person Time on Treatment

The total person time on albiglutide treatment (in years) is defined as the total time on study medication between the time of the last dose date and the first dose date plus 26 days (to account for the long half-life of albiglutide) and then divided by 365.25 days/year.

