6.2. Disposition of Subjects

The number of subjects who were randomized and the number of subjects within each population (ITT, Safety, PP, PK) will be summarized for each treatment group. A summary of subjects randomized by geographic region, and site will also be provided by treatment group.

The numbers and percentages of subjects who completed the study, discontinued the study, and discontinued the study treatment, along with reasons for discontinuation, will be summarized by treatment group. Additionally, among subjects who completed the study the number and percentage of subjects who continued into the open-label extension study, and did not participate in the open-label extension study will be also summarized and tabulated.

Subject status by visit summary will be provided.

Subject disposition data will be listed as well. All disposition summaries will be based on the all randomized subjects.

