8.2.2. Injection Site Reactions

Injection site reactions are reported by the investigators on the eCRF. The number and percentage of subjects with injection site reactions and 95% confidence intervals of the proportions will be presented by treatment group. In addition, the time to first occurrence of an injection site reaction will be analyzed and presented in a manner identical to that described for the first occurrence of a GI event in Section 8.2.7.5.

The number and percentage of subjects reporting injection site reactions at each study week will be presented by treatment group. Each week will include those subjects with the onset of an injection site reaction during that particular week as well as those subjects with injection site reactions from previous weeks that have not resolved. The incidence of injection site reactions will be plotted over time. Various characteristics of injection site reactions at the event level and subject level will be summarized.

A by-subject listing of injection site reactions will also be produced.

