8.2.7.5. Gastrointestinal (GI) Events

A summary of the number and percentage of subjects with GI events (specifically, AEs coded to the MedDRA SOC of gastrointestinal disorders) will be reported by treatment

group and therapeutic phase (pre-, on-, or post-therapy). Also, summaries of on-therapy GI events that lead to withdrawal of active treatment, treatment-related and serious GI events (including those that do not necessarily lead to withdrawal of active treatment) will be presented separately by treatment group.

For each subject, the time to first occurrence of a GI event is calculated as the number of days between the randomization date and the date of onset of the first on-therapy GI event plus 1. Subjects who do not experience any GI events will be censored at the last dose date + 25 days. The median time to first occurrence of a GI event as well as the Kaplan-Meier probability of first occurrence of a GI event at various time points will be presented for each treatment group.

The prevalence of GI events will be reported and plotted by treatment group.

The number and percentage of subjects reporting nausea at each study week will be presented by treatment group. Each week will include those subjects with onset of nausea during that particular week and also those subjects with nausea that started during a previous week but has not resolved. The prevalence of nausea will also be plotted over time. Similar summaries and plots will be presented for subjects reporting events of diarrhea and also separately for subjects reporting events of vomiting. In addition, a combined summary and accompanying plot of the number and percentage of subjects reporting events of nausea and/or vomiting will be presented.

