11. Once the HbA_{1c} results have been received from the central laboratory and all other eligibility criteria are met, study centre personnel will call the IVRS to obtain the subject's treatment assignment.
12. Subjects who discontinue study treatment should be handled as described in Protocol Section 5.5.
13. The end of treatment visit in Study 200952 is also Visit 1 of 204682 for those subjects continuing into the extension study.
14. Follow-up visit for subjects who have stopped investigational product (see Protocol Section 5.5), withdrawn from the study or who have completed the 26 week treatment period, but do not consent and/or are not eligible to participate in the 26 week extension study (Study 204682).
15. All visits will have a treatment window as in the table. Baseline (Week 0) serves as the reference point. Subjects will not be considered out of compliance if visit windows extend because of extraordinary events that make it impossible for subjects to complete a visit within the above window (e.g., holidays, vacations, personal emergencies). Determination of the maximum visit window deviation is at the discretion of the medical monitor

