11.5.4. AE (Event) Density and Incidence Rate

AE density, also referred to as event density, will be calculated as the number of events in a given period divided by the total person time on treatment (in years) of subjects at risk at the beginning of the same period. The incidence rate for an AE will be calculated as the number of subjects experiencing that AE within a given period divided by the total person time on treatment (in years) of subjects at risk at the beginning of the same period.

To enhance the data presentation and to aid comparison between treatment groupings, all AE densities and all incidence rates of AEs will be presented per 100 person-years (by multiplying the above defined statistics by 100).

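### Safety person-time and Kaplan-Meier censoring are not capped at the end of observation, and incidence rates keep time after the first event, so the descriptive person-time rates tend to read low

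*SAP*

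**What the plan says.** **Denominator.** SAP 11.5.3 defines person-time as the time "between the time of the last dose date and the first dose date plus 26 days", giving the drug's long half-life as the reason.

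**Numerator window.** SAP 11.4 treats an adverse event as on-therapy if it starts on or after the first dose and "within 25 days after the date of last dose".

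**Kaplan-Meier.** SAP 8.2.7.5 states: "Subjects who do not experience any GI events will be censored at the last dose date + 25 days". SAP 8.2.2 carries this over: "the time to first occurrence of an injection site reaction will be analyzed and presented in a manner identical to that described" for GI events. SAP 8.2.7.6 does the same for systemic allergic reactions.

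**Rollover.** SAP 11.3.4 puts the completer's last dose at Week 25. SAP 11.2.1, footnote 13, says: "The end of treatment visit in Study 200952 is also Visit 1 of 204682 for those subjects continuing into the extension study". SAP 2.3.2 reserves the 8-week follow-up for subjects who do not enter the extension. SAP 6.2 tabulates those who "continued into the open-label extension study".

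**Incidence rate.** SAP 11.5.4 takes "the number of subjects experiencing that AE within a given period divided by the total person time on treatment" of those at risk when the period starts. SAP 8.2.7 words the risk set slightly differently, as those at risk within the period. Neither stops a subject's clock at the first event.

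**The concern.** A person-time rate is sound when its denominator covers the time in which an event would have been recorded. Here the denominator and the Kaplan-Meier risk set run to 25 days after the last dose for everyone, whether or not this study was still observing the subject. For a completer who rolls over, observation in this study ends 7 days after the last dose. The remaining days are either unobserved, which makes the rate too low, or filled with events from an open-label study, which are then charged to the randomized arm. The SAP does not say which.

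The incidence rate has a second, separate feature. It counts each affected subject once but keeps dividing by time after the event, when that subject can no longer add to the numerator. The understatement grows with incidence, so it does not cancel between arms that differ. In a trial comparing two formulations, a rate ratio pulled toward 1 is the less cautious error.

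**Working it through.** **1. The 26 days.** 25-day on-therapy window (SAP 11.4) + 1 day for inclusive counting = 26. Denominator and numerator windows agree by design.

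**2. A completer who rolls over.** SAP 11.3.4 gives the Week 25 visit as Day 176 and the Week 26 visit as Day 183.
- Credited: 176 − 1 + 26 = 201 days.
- Observed in this study: 183 − 1 + 1 = 183 days.
- Excess: 201 − 183 = 18 days; 18/201 = 9.0%.

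**3. Effect on rates if extension events are excluded.** With a fraction *r* of completers rolling over (not given in the documents; assumed), planned rate ÷ capped rate = [183*r* + 201(1 − *r*)]/201.

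| *r* | ratio | understatement |
|---|---|---|
| 0 | 1.000 | none |
| 0.50 | 0.955 | 4.5% |
| 1.00 | 0.910 | 9.0% |

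Now add the 13% early loss assumed in the sample size section (SAP 11.12.1). Assume that these subjects leave at Week 12 (Day 85) with no later contact; each is then credited 110 days and observed for 85. The understatement is 1.7% if none of the rest roll over and 10.0% if all do.

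**4. Time after the first event.** Under a constant hazard, planned incidence rate ÷ first-event rate = *p*/[−ln(1 − *p*)]. For illustration only, *p* is taken from the injection site reaction figures in Protocol 4.6.1, Table 2 (14% antibody-negative, 41% antibody-positive). The denominator is 201/365.25 = 0.550 years.

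| *p* | planned, per 100 person-years | first-event, per 100 person-years | understatement |
|---|---|---|---|
| 14% | 25.4 | 27.4 | 7.2% |
| 41% | 74.5 | 95.9 | 22.3% |

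Effect on a ratio, with assumed arm incidences:
- 25% vs 15%: ln(0.75)/ln(0.85) = 1.77; planned 25/15 = 1.67.
- 30% vs 15%: ln(0.70)/ln(0.85) = 2.19; planned 30/15 = 2.00.

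**5. Both together, all completers rolling over.** 14% incidence: 25.4 vs 30.1 (15.5% low). 41%: 74.5 vs 105.3 (29% low).

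**6. Kaplan-Meier.** Simulation of 20,000 subjects with a constant hazard set to give 14% or 41% by Day 183; 13% leave at a random weekly dose with no later contact, and 50% or 100% of the rest roll over.
- At Day 183 the cumulative probability is 0.2 to 0.6 percentage points low.
- At Day 201 with 50% rollover it is 0.8 points low (14.7% vs 15.5%) to 2.1 points low (41.9% vs 44.0%).

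Late censoring of rollover subjects acts only after Day 183. Before that, only early leavers contribute.

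**7. Between arms.** If rollover is similar, the effect in step 3 cancels in a rate ratio. With 90% in one arm and 50% in the other, the factors are 1 − 0.9 × 18/201 = 0.919 and 0.955. Their ratio is 0.96, so the rate ratio moves by under 4%.

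**The case against.** **The window is deliberate and matched.** The 26 days mirror the on-therapy window and rest on a half-life of about 5 days, with drug persisting for 3 to 4 weeks (Protocol 6.9). Subjects who stop drug are expected to keep attending (Protocol 5.5.1.1), and non-rollover completers have the Week 34 visit. This stands for everyone actually followed through the window: for them there is no bias. It does not help where events in the window are not collected by this study.

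**Extension data are mentioned.** SAP 8.2.1 says that safety and exposure of continuing subjects will be summarized too. It does not say whether those events enter the on-therapy numerators, so the question stays open.

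**The incidence rate is a declared crude rate.** This is fair. SAP 11.5.4 states its denominator ("divided by the total person time on treatment (in years) of subjects at risk at the beginning of the same period") and computes what it states. The gap between 1.77 and 1.67 is that between a hazard ratio and a risk ratio, and it depends on a constant hazard. The remaining objection is that a figure labelled per 100 person-years will be read as a rate among those still at risk.

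**Stronger readings a reader might infer.** One is that rollover shrinks a real formulation difference. The documents do not support this: only subjects who stayed on product may roll over, so a better-tolerated arm could roll over more. Its rates would then be lowered more and the difference enlarged. Another is that GI and injection site reaction rates are understated. For those events SAP 8.2.7.5 and 8.2.2 specify percentages and Kaplan-Meier summaries, not person-time rates.

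**Conclusion.** The point holds, and it is small. The uncapped rules lower exposure-adjusted rates by up to 9% when all completers roll over and by 4.5% at an assumed 50%, provided extension events are excluded. If extension events are included, the problem becomes one of attribution. The effect mostly cancels between arms when rollover is similar, and its direction on the arm difference cannot be predicted. Kaplan-Meier estimates at Week 26 move by less than 1 percentage point.

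Keeping time after the first event lowers the incidence rate by about 7% at 14% incidence and 22% at 41%, and pulls rate ratios toward 1 when incidences differ. Event density rightly keeps that time.

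The outputs affected are the person-time rates in the adverse event overview, for selected events of special interest and for hypoglycemia, and slightly the Kaplan-Meier tables. All are descriptive; Protocol 9.4.2 plans no inferential testing on safety. It would be wrong to infer that the main comparability results are compromised: the HbA1c analysis, and the injection site reaction and antibody proportions with their confidence intervals, do not use these denominators.

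The sizes rest on assumed rollover fractions, an assumed time of early loss, a constant hazard, and incidences borrowed for illustration.

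**What to change.** - **SAP 11.5.3, 11.4 and 8.2.7.5:** end person-time, on-therapy event counting for rate numerators, and Kaplan-Meier censoring at the earliest of last dose + 25 days, entry into Study 204682 (one date, the Week 26 visit), death, and last contact in this study. The Kaplan-Meier change carries through to 8.2.2 and 8.2.7.6.
- **SAP 8.2.1:** state that extension adverse events are reported separately and do not enter these rates.
- **SAP 11.5.4:** for the incidence rate, end each subject's person-time at first onset of that event, and align 8.2.7 with this. Leave event density unchanged.

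The cost is SAP wording and one derivation from dates already collected; trial conduct does not change. The rates become slightly less comparable with earlier reports, so the old definition can be shown alongside.
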